### **6.2.5 Open-Label Visit: Visit 6 (Day 71 ±3)**

The following will be performed/collected at Visit 6:

- physical examination, including weight
- vital signs (blood pressure and pulse rate)
- clinical safety laboratory assessment: chemistry, hematology, standard urinalysis only
- concomitant medication review

- serum CRP
- Clinical Response Score ([Table 2](#)), based on subject recording of stool frequency and rectal bleeding in the daily diary
- IBDQ
- assessment of any AEs since the previous visit
- review of subject daily diary data including compliance

#### **6.2.6 Open-Label End-of-Treatment Visits: Visit 7 (Day 113 -6) and Visit 8 (Day 113 ±3)**

The following will be performed/collected at Visit 7 (Day 113 – 6) or early withdrawal:

- estimated creatinine clearance
- clinical safety laboratory assessment: liver function tests (LFTs) and hematology
- Clinical Response Score ([Table 2](#)), based on subject recording of stool frequency and rectal bleeding in the daily diary
- flexible sigmoidoscopy/colonoscopy (at least 4 days prior to Visit 8 to allow sufficient time for the central reading)
- submit flexible sigmoidoscopy/colonoscopy recording to the independent central reader

The following will be performed/collected at Visit 8 (Day 113 ±3) or early withdrawal:

- physical examination, including weight
- vital signs (blood pressure and pulse rate)
- 12-lead ECG
- urine pregnancy testing (test strip) for females of childbearing age or <1 year postmenopausal (if positive, the subject will not be enrolled in Study 000175)
- clinical safety laboratory assessment: chemistry, hematology, coagulation, standard urinalysis
- concomitant medication review
- serum CRP and fecal calprotectin levels
- calculation of Clinical and Endoscopic Response Score ([Table 2](#)).
- IBDQ
- assessment of any AEs since the previous visit
- collection of trial medication

- review of subject daily diary data including compliance, and deactivation of subject daily diary
- trial medication compliance assessment

## 7 TRIAL ASSESSMENTS

### 7.1 Assessments Related to Endpoints

#### 7.1.1 Clinical and Endoscopic Response Score and Physician's Global Assessment

The Clinical and Endoscopic Response Score will be determined, as shown in [Table 2](#).

The Modified Mayo score will be calculated as the sum of the Clinical and Endoscopic Response Scores ([Table 2](#)) and the PGA score ([Table 3](#)).

The Endoscopic Response Score will be determined by flexible sigmoidoscopy/colonoscopy as scored by the independent central reader (Section [7.1.2](#)).

The scores on stool frequency and rectal bleeding will be obtained from the subject electronic daily diary, with the exception of screening which will be based on subject recall (Section [7.1.3](#)).

The Modified Mayo score will be calculated by the investigator at baseline/randomization, and at the end of double-blind treatment (Week 8 or early withdrawal).

**Table 2: Clinical and Endoscopic Response Score (0 – 9)**

Components	Subscale	Severity	Score
CLINICAL RESPONSE  (Subject's Symptoms)	Stool Frequencya (daily)	Normal number of stools for subject	0
		1 to 2 stools more than normal	1
		3 to 4 stools more than normal	2
		≥5 stools more than normal	3
	Rectal Bleedingb (daily)	No blood seen	0
		Streaks of blood with stool	1
		Obvious blood with stool	2
		Blood alone passes	3
ENDOSCOPIC RESPONSE  (Objective Evidence of Inflammation)	Flexible Sigmoidoscopy /colonoscopy Findings	Normal or inactive disease	0
		Mild disease (erythema, decreased vascular pattern, granularity)	1
		Moderate disease (marked erythema, absent vascular pattern, any friability, erosions)	2
		Severe disease (spontaneous bleeding, ulceration)	3

Adapted from: Schroeder et al., 1987 (1); Sninsky et al., 1991 (2); Modified by Ferring Group, 2014

a. Each subject serves as his or her own control to establish the degree of abnormality of the stool frequency.

b. The daily bleeding score represents the most severe bleeding of the day.

**Table 3: Physician's Global Assessment**

Severity	Score
Normal	0
Mild disease	1
Moderate disease	2
Severe disease	3

### 7.1.2 Flexible Sigmoidoscopy/colonoscopy

In order to obtain the endoscopic response score (Table 2), the objective evidence of inflammation in this trial, flexible sigmoidoscopy/colonoscopy will be performed according to a standardized manner during screening (no more than 10 days but at least 4 days prior to randomization to allow sufficient time for the central reading), the end of double-blind treatment (Week 8 or early withdrawal), and at the end of open-label treatment. Flexible sigmoidoscopy/colonoscopy will be video recorded and transferred to the independent central reader. The details of the tools, recording, data transfer, and assessment will be documented in an imaging charter. Findings will be graded on a 4-point scale (Table 2), with 0 = normal or inactive disease, 1 = mild disease (erythema, decreased vascular pattern, granularity), 2 = moderate disease (marked erythema, absent vascular pattern, any friability, erosions), and 3 = severe disease (spontaneous bleeding, ulceration). The flexible sigmoidoscopy/colonoscopy recording during screening will be sent to the independent central reader for final determination of eligibility, regardless of the local site's score. A flexible sigmoidoscopy/colonoscopy will also be performed at Weeks 8 and 16 as applicable. These recordings will also be sent to the independent central reader for endoscopic endpoint scoring. A colonoscopy will be required to establish the extent of disease if the flexible sigmoidoscopy is not conclusive in establishing the upper border of UC involvement. Extent of colitis will be documented as proctosigmoiditis, left-sided colitis, or extended colitis.

#### 7.1.2.1 Independent Central Endoscopy Laboratory

All flexible sigmoidoscopies and colonoscopies (if required), will be performed in a standardized manner. The endoscopy completed during screening (no more than 10 days but at least 4 days prior to randomization to allow sufficient time for the central reading), at Week 8 (end of double-blind treatment/early withdrawal), and Week 16 (end of open-label treatment/early withdrawal) will be sent to the independent central reader selected by the sponsor. The screening result will be used to qualify the image for use in randomization. Image handling and instructions will be provided to all sites directly from the independent central laboratory.

The endoscopic qualifying score will be automatically uploaded to the eCRF.

Trial sites will be provided with endoscopic laboratory recording equipment, supplies, and manuals.

### **7.1.3 Subject Daily Diary**

The subject daily diary will be completed by the subject every evening starting the day of randomization (Visit 1/Day 1). Subject diary will consist of questions regarding IMP daily intake, stool frequency, and presence of blood content. The score for stool frequency and rectal bleeding will be calculated as an average based on scores collected from 3 day subject recall at Visit 0 or from subject diary data 5 days prior to Visits 2, 3, 4, 6 and 7 (see [Appendix 2](#)). If a subject recorded fewer than 3 days of scores during this 5-day period, the average score will be considered missing.

The subject daily diary and questionnaire will be completed via a validated Interactive Voice Response system (IVRS). Instructions on the use of the subject daily diary and questionnaire will be provided to each trial center.

### **7.1.4 Serum CRP and Fecal Calprotectin**

Serum CRP levels will be determined at baseline and Visits 2 (Week 2), 3 (Week 4), 5 (Week 8) during the double-blind treatment period, and at Visits 6 (Week 10) and 8 (Week 16) during the open-label treatment period. Fecal calprotectin levels will be determined at baseline and at Visit 5 (Week 8) of the double-blind treatment period and at Visit 8 (Week 16) of the open-label treatment period.

### **7.1.5 Health-Related Quality of Life/Collection Pad**

The IBDQ is an instrument used to assess quality of life in adult patients with inflammatory bowel disease, UC, or Crohn's disease and has demonstrated reliability and validity in discriminating between patients in clinical remission or relapse. (18) Subjects will be asked to recall symptoms and quality of life from the last 2 weeks and to rate each item on a 7-point Likert scale (higher scores equate to higher quality of life). Subjects will complete the IBDQ questionnaire (see [Appendix 1](#)) via a validated collection pad, prior to all other trial-related procedures at the site at Visit 2 (Week 2), Visit 3 (Week 4), and Visit 5 (Week 8) (or early withdrawal) during the double-blind treatment period, and at Visits 6 (Week 10) and 8 (Week 16) during the open-label treatment period (after randomization but before IMP administration). At Visit 1, subjects must first be randomized before completion of the IBDQ.

### **7.1.6 Adverse Events**

Adverse events will be collected as described in Section 8 of this protocol.

Laboratory abnormalities may be reported as AEs based on the discretion of the investigator, i.e., laboratory abnormalities that the investigator assesses as a clinically significant.

Physical examination and vital sign abnormalities will be reported as AEs if the investigator considers any abnormality clinically significant.

## **7.1.7 Clinical Laboratory Variables**

### **Hematology, Serum Chemistry, and Urinalysis**

Safety hematology, coagulation, and serum chemistry tests will be performed at Visit 0 (screening), Visits 4 and 5 (Week 8) or at early withdrawal during the double-blind treatment period, Visit 6 (Week 10) and Visits 7 and 8 (Week 16) during the open-label treatment period.

Hematology: hematocrit, hemoglobin, platelet count, red blood cell count, white blood cell count, and differential count

Coagulation: prothrombin time (measured as international normalized ratio), activated partial thromboplastin time

Serum chemistry: glucose, blood urea nitrogen, creatinine, creatinine clearance (via estimated glomerular filtration rate [eGFR]), potassium, sodium, chloride, calcium, total protein, albumin, total bilirubin, alkaline phosphatase, aspartate aminotransferase, alanine aminotransferase, and gamma glutamyl transferase

Urinalysis: leukocyte, blood, pH, specific gravity, nitrite, protein, glucose, urobilinogen, and microscopic if positive for blood, leucocytes, and nitrite

The investigator will review the laboratory results and evaluate and document whether the results are normal or abnormal and whether abnormal results are clinically significant. The laboratory report will be signed and dated by the investigator.

## **7.2 Other Assessments**

### **7.2.1 Medical History and Demographic Data**

Demographic data and a complete medical history will be obtained at Visit 0 (screening), with a review of medical history at Visit 1 (baseline/Day 1). Disease specific and general medical history will be recorded in the eCRF.

### **7.2.2 Immunological Testing**

Serological testing for HBV, HCV, and HIV will be performed at Visit 0 (screening). Negative results are required for trial admission.

### **7.2.3 Drug and Alcohol History**

At Visit 0 (screening), a drug and alcohol history evaluation will be performed by the investigator.

#### **7.2.4 Serum/Urine Pregnancy Test**

A serum pregnancy test will be performed at Visit 0 (screening). A urine pregnancy test will be performed at Visit 1 (baseline/Day 1) and Visit 5 (Week 8) or early withdrawal during the double-blind treatment period and at Visit 8 (Week 16) of the open-label treatment period (Table 1). Negative results are required for admission to each period.

#### **7.2.5 Screening Stool Sample**

A stool sample will be obtained at screening to rule out parasites, bacterial pathogens, and *Clostridium difficile*. Subjects who test positive for *Clostridium difficile* can be rescreened if treated and *Clostridium difficile* negative for 2 consecutive months.

#### **7.2.6 Concomitant Medications**

Concomitant medication information will be collected at every trial visit during the double-blind and open-label treatment periods (Table 1).

#### **7.2.7 Physical Examinations**

At the screening visit (Visit 0), physical examination with height and weight will be performed. Height will be measured at the screening visit only. Physical examination with weight will be performed at Visit 1 (baseline/Day 1), Visit 2 (Week 2), Visit 3 (Week 4), and at the end of double-blind treatment Visit 5 (Week 8 [or at early withdrawal]), as well as during open-label treatment period Visits 6 and 8 (Weeks 10 and 16 [or at early withdrawal]) (Table 1). Any clinically significant deterioration from baseline will be recorded as an AE.

#### **7.2.8 Vital Signs**

Vital signs will be measured at each trial visit except Visits 4 and 7 (Table 1). Vital signs will include blood pressure and heart rate measured under resting conditions while the subject is seated. All blood pressure measurements should be made using the same arm and prior to any scheduled blood draws.

#### **7.2.9 12-Lead Electrocardiogram**

A 12-lead ECG will be obtained at Visit 0 (screening) and Visit 5 (Week 8) or at early withdrawal during the double-blind treatment period and at Week 16 (or at early withdrawal) of the open-label treatment period (Table 1). The 12-lead ECG will be obtained after at least a 5-minute rest in a supine position.

#### **7.2.10 Compliance**

Trial medication and subject daily diary compliance will be assessed at Visit 2 (Week 2), Visit 3 (Week 4), and Visit 5 (Week 8) or at early withdrawal during the double-blind treatment period and at Visit 8 (Week 16 [or at early withdrawal]) during the open-label treatment period (Table 1). Subject

daily diary compliance will also be assessed at Visit 6 (Week 10) during the open-label treatment period.

### **7.3 Drug Concentration Measurements**

Drug concentration measurements will not be performed for this trial.

### **7.4 Handling of Biological Samples**

A central laboratory will be used in this trial. Sampling tubes, material for shipment of the samples, and a laboratory manual detailing all sample collection, handling and shipment procedures will be provided and distributed to the trial sites by the central laboratory.

## **8 ADVERSE EVENTS**

### **8.1 Adverse Event Definition**

An AE is any untoward medical occurrence in a subject participating in a clinical trial. It includes:

- any unfavorable and unintended sign, symptom or disease temporally associated with the use of the IMP, whether or not considered to be caused by the IMP
- AEs commonly observed and AEs anticipated based on the pharmacological effect of the IMP
- any laboratory abnormality, vital sign, or finding from physical (or gynecological) examination assessed as clinically significant by the investigator (note: findings from assessments and examinations done during screening are not AEs, but are recorded as medical history)
- accidental injuries, reasons for any change in medication (drug and/or dose), reasons for any medical, nursing or pharmacy consultation, or reasons for admission to hospital or surgical procedures
- overdoses and medication errors with and without clinical consequences

### **8.2 Collection and Recording of Adverse Events**

#### **8.2.1 Collection of Adverse Events**

The investigator must monitor the condition of the subject throughout the trial from the time of obtaining informed consent until the last visit.

The sources of AEs cover:

- the subject's response to questions about his/her health (a standard non-leading question such as "How have you been feeling since your last visit?" is asked at each visit)
- symptoms spontaneously reported by the subject
- investigations and examinations where the findings are assessed by the investigator to be clinically significant changes or abnormalities
- other information relating to the subject's health becoming known to the investigator (e.g. hospitalization)

#### **8.2.2 Recording of Adverse Events**

The investigator must record all AEs in the AE log provided in each subject's eCRF with information about:

- AE

- date and time of onset (time can be omitted, if applicable)
- intensity
- causal relationship to IMP
- action taken to IMP
- other action taken
- date and time of outcome (time can be omitted, if applicable)
- outcome
- seriousness

Each of the items in the AE log is described in detail in the following sections.

### **Adverse Events**

Adverse events should be recorded as diagnoses, if available. If not, separate signs and symptoms should be recorded. One diagnosis/symptom should be entered per record.

If a subject suffers from the same AE more than once and the subject recovers between the events, the AEs should be recorded separately. If an AE changes in intensity, a worst-case approach should be used when recording the event, i.e. the highest intensity and the longest duration of the event.a

A procedure is not an AE; the reason for conducting the procedure is. Hospitalization is not an AE; the reason for hospitalization is. Death is not an AE, but the cause of death is (an exception is sudden death of unknown cause, which is an AE).

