Subjects who are found to be worse, defined by an increased number of bowel movements (BM), blood in the stool, abdominal pain and distention, or clinically relevant changes in laboratory chemistry and/or hematology on or after Week 2 will be offered early escape during the trial before Week 8 and will be treated by local standard of care. Subjects who complete Week 8 but fail to meet the defined criteria for remission will be given an option to receive open-label treatment with mesalamine 4 g extended release granules (sachet) for 8 additional weeks in the current trial. If subjects do not opt to receive the 8-week open-label mesalamine treatment, they will be treated by local standard of care. If subjects opt to receive the additional 8-week open-label mesalamine treatment, they will continue with daily diary entries and visit the trial site at 10 and 16 weeks, with only a Clinical Response Score assessment at Week 10, and a Clinical and Endoscopic Response

Score assessment performed at Week 16 in order to determine the subject's eligibility for entry into the maintenance trial (Study 000175).

[figure not shown]
Flexible sigmoidoscopy/colonoscopy will be video recorded and transferred to the independent central reader. The details of the tools, recording, data transfer, and assessment will be documented in an Imaging Charter. The flexible sigmoidoscopy/colonoscopy recording during screening will be sent to the independent central reader for final determination of eligibility, regardless of the local site's score. A flexible sigmoidoscopy/colonoscopy will also be performed at Weeks 8 and 16 as applicable. These recordings will also be sent to the independent central reader for endoscopic endpoint scoring.

Subjects from either treatment group who meet the defined remission criteria after the 8-week double-blind treatment period will be allowed to enroll into a double-blind trial investigating maintenance therapy of mesalamine 2 g extended release granules (Study 000175). Those subjects who do not achieve remission after the 8 additional weeks of open-label treatment will not be enrolled into Study 000175 and will be treated with the local standard of care.

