### **Date and Time of Onset**

The date of onset is the date when the first sign(s) or symptom(s) were first noted. If the AE is an abnormal clinically significant laboratory test or outcome of an examination, the onset date is the date the sample was taken or the examination was performed.

---

a Exception: if an AE with onset before the first IMP administration (i.e., a pre-treatment AE) changes in intensity, this must be recorded as 2 separate events. The initial AE should be recorded with outcome “not yet recovered” and the date and time of outcome are when the intensity changed. The second AE should be recorded with date and time of onset when the intensity changed.

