6.4 Safety Analysis Set

The safety analysis set includes all subjects who receive at least one dose of IMP. Safety analyses will be conducted according to the treatment actually received.

7 Trial population

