10.2 Adverse Events

Adverse events (AEs) will be classified according to the MedDRA version 17.1 or later.

Written narratives will be issued for all serious AEs (including deaths) and AEs leading to discontinuation.

A 'pre-treatment' AE will be defined as an AE that occurs between screening and the first dose of the IMP. A 'treatment-emergent AE (TEAE)' will be an AE which occurs in the time interval from initial dosing (IMP intake) to the end of treatment visit. If an AE on Day 1 occurs before IMP intake, it will be recorded as a pre-treatment AE. An AE that occurs after the first dose of the open-label period will be considered a TEAE for the open-label period.

If causality is missing, the AE will be regarded as being reasonably possibly related to IMP. Related AEs (judged as being reasonably possibly related to IMP) will be termed adverse drug reactions (ADR).

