10.2.2 Incidence of Adverse Events

The summaries will include the total number of subjects reporting an AE, the percentage of subjects (%) with an AE, and the number of events (E) reported. AEs will be presented by SOC sorted alphabetically and PT sorted in decreasing frequency of occurrence.

Summary tables will be prepared for:

- Any TEAEs
- Common TEAEs, defined as TEAEs with an incidence $\geq 2\%$ of subjects in any treatment group
- Any TEAEs by causality (related/unrelated)
- Any TEAEs by intensity
- Any AEs leading to death
- Serious adverse events
- Any TEAEs leading to discontinuation

Supporting data listings will be provided for:

- All adverse events sorted by trial site and subject ID
- All adverse events sorted by MedDRA SOC and PT
- Serious adverse events
- Adverse events leading to death
- Adverse events leading to discontinuation

A listing of SOC and PT for all unique verbatim will be provided.

For the open-label period, the following summaries and listings will be provided for subjects who receive the open-label treatment:

- Any TEAEs
- Any TEAEs by causality (related/unrelated)
- Any TEAEs by intensity
- Any AEs leading to death
- Serious adverse events
- Any TEAEs leading to discontinuation

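### An adverse event that starts in the double-blind period and worsens on open-label mesalamine is tabulated at its worst intensity in the double-blind tables, because the record is not split at the first open-label dose

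*Protocol*

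**What the plan says.** **Recording.** Protocol 8.2.2 (Adverse Events) keeps one record per event: "If an AE changes in intensity, a worst-case approach should be used when recording the event, i.e. the highest intensity and the longest duration". Under Date and Time of Onset, "The date of onset is the date when the first sign(s) or symptom(s) were first noted". Footnote a gives the only exception, which reads: "if an AE with onset before the first IMP administration (i.e., a pre-treatment AE) changes in intensity, this must be recorded as 2 separate events". Among the items listed for the AE log in 8.2.2 there is one intensity entry and no date on which intensity changed.

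**Assignment to a period.** SAP 10.2 defines a treatment-emergent event as "an AE which occurs in the time interval from initial dosing (IMP intake) to the end of treatment visit" and adds: "An AE that occurs after the first dose of the open-label period will be considered a TEAE for the open-label period". It says nothing about an event already ongoing at that dose which then worsens.

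**Tables.** SAP 10.2.1 has a row for severe treatment-emergent events, and SAP 10.2.2 plans "Any TEAEs by intensity". Both sections provide corresponding open-label outputs. SAP 6.4 states: "Safety analyses will be conducted according to the treatment actually received".

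**Who switches.** Protocol 3.1.1: "Subjects who complete Week 8 but fail to meet the defined criteria for remission will be given an option to receive open-label treatment". This applies to both arms. Protocol 3.5.5 puts the first open-label dose on the day after double-blind treatment ends.

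**The concern.** Worst-case recording is sound while treatment does not change. Here treatment can change at Week 8, and for placebo subjects it changes from placebo to active drug. A record that keeps the double-blind onset but takes its intensity from the open-label period describes two treatments at once, and the tables can place it under only one.

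The plan already accepts this reasoning at the first change of treatment. Footnote a splits a pre-treatment event that changes intensity, so that the part on treatment has its own onset. The second change of treatment has no such split.

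The incidence and severity of adverse events is both a stated secondary objective (Protocol 2.1) and a secondary endpoint (Protocol 2.2). At stake are the double-blind comparison by intensity and the completeness of the open-label tables. Intensity at the switch is not among the listed log items, so the planned dataset cannot reliably separate the two parts afterwards.

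**Working it through.** **1. Follow one event through the rules.** Take a hypothetical placebo subject with mild headache from Day 50. The subject is not in remission at Week 8, starts open-label mesalamine, and the headache becomes severe on Day 65.

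- Protocol 8.2.2: one record, intensity severe, onset Day 50.
- Footnote a: does not apply, because onset was after the first dose of study drug.
- SAP 10.2: onset lies in the double-blind period, and no rule moves the worsening to open label.
- SAP 10.2.1 and 10.2.2: a severe event in the double-blind placebo column, and no event in the open-label tables.

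For a subject randomized to mesalamine the path is the same, but the drug does not change. The 8-week table then carries severity from as late as Week 16. That is an error of period, not of drug.

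**2. Check the planning figures.** Inputs from Protocol 9.1: 110 per arm, remission 36% and 18%, two-sided 0.05 chi-square test, at least 85% power. With mean proportion 0.27:

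- Power = Φ{[0.18 × √110 − 1.96 × √(2 × 0.27 × 0.73)] / √(0.36 × 0.64 + 0.18 × 0.82)} = Φ(1.07) = 85.7%.

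The stated power reproduces.

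**3. How many subjects could switch.** Protocol 9.6.2 counts discontinuers as non-remitters, but open label requires completing Week 8. So the maximum number of entrants is 110 × (1 − remission rate − dropout). The documents give no dropout rate; the values below are assumptions.

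| Dropout, mesalamine / placebo | Mesalamine | Placebo | Placebo share |
|---|---|---|---|
| 0% / 0% | 70.4 | 90.2 | 56% |
| 10% / 10% | 59.4 | 79.2 | 57% |
| 20% / 20% | 48.4 | 68.2 | 58% |
| 10% / 20% | 59.4 | 68.2 | 53% |
| 10% / 28% | 59.4 | 59.4 | 50% |

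With equal opt-in, the arms balance when 0.82 − placebo dropout = 0.64 − mesalamine dropout, that is, when placebo dropout is higher by 18 points.

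**4. Size of the distortion.** Let q be the share of open-label entrants with a double-blind-onset event that becomes severe in open label. The documents give no q, so a range of 1% to 5% is assumed, with 10% dropout per arm, full opt-in, and no other severe double-blind event in these subjects.

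- Placebo inflation = q × 79.2/110 = 0.72q, or 0.7 to 3.6 points.
- Mesalamine inflation = q × 59.4/110 = 0.54q, or 0.5 to 2.7 points.
- Spurious gap against placebo if q is equal in the arms = 0.18q, or 0.2 to 0.9 points.
- Gap if only newly exposed placebo subjects worsen = 0.72q, or 0.7 to 3.6 points.

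**The case against.** **Other wording might cover the switch.** Protocol 3.5.5 calls the first open-label dose the first dose of IMP, so a site could try to apply footnote a there. But the footnote equates its scope with pre-treatment events, which SAP 10.2 defines as falling between screening and the first dose. The protocol synopsis counts a pre-existing condition that worsens after the start of IMP as treatment-emergent; that is tied to the start of IMP and is not repeated in Protocol 9.8.2 or SAP 10.2. The SAP says that an event occurs, not that it has onset, so its period rule is best called silent on worsening. Even a generous reading leaves a single record with one intensity and the first-symptom date. Nor does tabulating by treatment actually received help, since there is no second record to place.

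**Serious cases remain visible.** This stands in large part. Serious events and events leading to discontinuation receive narratives and listings (SAP 10.2 and 10.2.2). A reader might infer that the rule hides harm. The documents do not support that: what is misplaced is mainly non-serious worsening in descriptive tables.

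**The rule is narrower than it may look.** This stands. A reader might extend the point to causality, outcome and action taken. The worst-case rule names only intensity and duration, and the documents do not say how changes in those other entries are handled.

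**The change comes late.** This also stands. The SAP rests on a consolidated protocol dated January 2017, and Protocol 3.1.3 expects the last visit in the third quarter of 2017. A new split could leave earlier and later subjects recorded differently unless earlier records are queried or listed.

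**Conclusion.** The gap is real. Followed as written, the plan puts worsening on open-label mesalamine into the double-blind intensity and severe-event tables and leaves it out of the open-label tables. Severity is charged to the wrong treatment for placebo subjects only.

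A reader might take a placebo majority among the affected as given. It is an inference from the assumed 36% and 18% remission rates with similar dropout and opt-in, and it would not hold if remission were equal in the arms. A reader might also count every event ongoing at the switch as an error. Such an event is only exposed to the rule; it must also worsen after the switch to be misplaced.

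At 10% dropout per arm, and with 1% to 5% of entrants affected, the inflation is about 0.7 to 3.6 points on placebo and 0.5 to 2.7 on mesalamine. These rates are illustrations, not estimates. The effect is probably small, and the primary analysis and sample size are not touched. It is still worth correcting, because a stated rule gives a wrong result on a stated secondary endpoint.

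**What to change.** 1. **Protocol 8.2.2, footnote a.** Extend it: an event ongoing at the first open-label dose that later increases in intensity or becomes serious is recorded as 2 events, the second with onset at the date of change. Becoming serious is included because seriousness is also a single log item.
2. **SAP 10.2.** State that the second record is an open-label treatment-emergent event and that only the first record enters the double-blind tables.
3. **Records already entered.** List events with double-blind onset that were ongoing at the first open-label dose, using the onset and outcome dates already collected, and flag them in the intensity tables.

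The cost is one sentence in each document, a few extra event records, and queries or a listing for subjects recorded under the present rule. Sites already apply the same kind of split at the first dose.
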